#### **4. Participant Selection and Enrollment**

Participants will be recruited by referral from an ongoing NIH funded study. The parent study aims to prevent HCV among young current PWID (R01DA041501). Potential enrollees for the parent study will receive baseline HCV antibody testing, and those that test positive will be referred to ST&RT.

Participants willing to enroll may be offered a same-day or next business day visit to assess for eligibility. If eligible for ST&RT, participants will receive informed consent. Ineligible participants may be offered enrollment into other ongoing studies. We do not expect to enroll participants from other referral sources for this study; however, participants meeting the inclusion criteria from other sources will also be considered if otherwise eligible. For participants enrolling in part B, enrollment may occur in person or remotely (i.e. without person to person contact).

## 5 Study Procedures

### 5.1 Schedule of Events during Part A:

	Screening (performed by parent study)	Entry		On-Treatment				Post-Treatment								Additional tests if Treatment interruption	Additional tests if Reinfection or Relapse
		Week 0		Week 4		Week 12		Week 16		Week 24		Week 36		Week 48			
Randomized Arm		Int.	Con.	Int.	Con.	Int.	Con.	Int.	Con.	Int.	Con.	Int.	Con.	Int.	Con.		
HCV Antibody	X																
Plasma HCV RNA PCR		X	X	X		X	X	X		X	X	X	X	X	X		
HIV-1/2 Antibody	X									X	X			X	X		
Hepatic Function Panel		X		X†		X†				X†				X†			
Hematology (CBCC)		X								X†							
Basic Metabolic Panel		X		X†													
Weight		X															
FIB-4 (calculated)		X															
Hepatitis B panel		X															
Pregnancy Test (female participants)		X		X*†		X*†											
HCV genotyping		X														X†	
Physical Exam		X		X*†		X*†											
Adherence Assessment				Weekly for Int. arm†													

Reinfection Prevention counseling				Once for int. arm †												
Questionnaire and Interview		X	X			X	X		X	X	X	X	X	X		
Stored serum / plasma**		X	X			X	X	X	X	X	X		X	X		X

\*If medically indicated

\*\*In event phlebotomy is unavailable or unsuccessful, dried blood spots may be obtained by finger stick

† HCV RNA PCR Positive participants only

Windows: week 4 has a window of -7 days or + 14 days; Week 12 and 16 have a window of +7 days. Weeks 24 and 36 have a window of -14 to +28 days, and Week 48 has a window of -14 days.

## 5.2 Schedule of Events during Part B:

	Screening (performed by parent study)	Entry	On-Treatment		Post-Treatment				Additional tests if Treatment interruption	Additional tests if Reinfection or Relapse
			Week 0	Week 4	Week 12	Week 16	Week 24	Week 36	Week 48	
Arm		Tel.	Tel.	Tel.	Tel.	Tel.	Tel.	Tel.	Tel.	
HCV Antibody	X									
Plasma HCV RNA PCR		X	X‡	X	X‡	X	X	X	X	
HIV-1/2 Antibody	X					X		X		
Hepatic Function Panel		X	X†‡	X†		X†		X†		
Hematology (CBCC)		X				X†				
Basic Metabolic Panel		X	X†‡							
Weight		X								
FIB-4 (calculated)	X									
Hepatitis B panel	X									
Pregnancy Test (female participants)		X	X*†‡	X*†						
HCV genotyping		X								X†
Physical Exam		*	*	*						
Adherence Assessment			Weekly †							
Reinfection Prevention counseling			Once†							

Questionnaire and Interview		X		X		X	X	X		
Stored serum / plasma**		X‡		X‡	X‡	X‡	X‡	X‡		X‡

\*If medically indicated

\*\*In event phlebotomy is unavailable or unsuccessful, dried blood spots may be obtained by finger stick

† HCV RNA PCR Positive participants only

‡ Optional Lab draw

Windows: week 4 has a window of -7 days or + 14 days; Week 12 and 16 have a window of +7 days. Weeks 24 and 36 have a window of -14 to +28 days, and Week 48 has a window of -14 days.

## 5.2 Laboratory evaluations

### 5.2.1 HCV RNA PCR

HCV RNA PCR will be collected and performed at a clinical laboratory (Roche Diagnostics COBAS TaqMan). HCV RNA PCR will be performed for all participants at each study visit, regardless of randomized treatment arm.

### 5.2.2 HIV-1/2 Antibody

Participants referred to ST&RT will be required to have a positive HCV antibody and negative HIV antibody test prior to consent and randomization. On-site HIV testing will be offered prior to entry to participants who do not already have a documented negative antibody. HIV retesting will be every 6 months thereafter, in keeping with recommendations for individuals at ongoing risk for acquisition. As necessary, patients will be referred for additional HIV testing, including testing for acute retroviral infection using HIV-1 RNA PCR

### 5.2.3 FIB-4

The FIB-4 score will be calculated from laboratory testing using the following formula:

$$\text{Fib-4} = \frac{\text{Age (years)} * \text{AST Level (U/L)}}{\text{Platelet count (10}^9/\text{L}) * \text{sq.rt.}(ALT(\text{U/L}))}$$

With a score of >3.25 representing advanced fibrosis.

### 5.2.4 Hepatitis B Panel

HBV testing will consist of HBV surface antigen, HBV surface antibody, HBV core antibody, HBV envelope antibody. HBV testing will be performed on all intervention participants at study entry.

### 5.2.5 Pregnancy Test

Serum beta-HCG will be performed for pregnancy test at study entry for all female participants, and may be performed again if there is concern for pregnancy. Participants of childbearing age will be provided contraceptive counseling, iterating the importance of contraception while on study medications.

## 5.3 Adherence Assessment

Adherence will be assessed for intervention group patients while on treatment. This will be accomplished by weekly secure text messaging consisting of a single item question.

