In this amendment, we will change the enrollment and analysis plans of our randomized study (called part A). This will involve conducting the analysis and reporting of comparative data between intervention and control arms, with the same study endpoints as the initial proposal. The main reason for ending enrollment at this time is the long delay we are likely to face before a co-located intervention can be offered in a physical syringe service program space. Instead, we will adapt our intervention to be telemedicine-based for continued enrollment into a nonrandomized treatment group (Part B). After the end of follow-up for part B, we will describe outcomes and compare to the previously randomized control population, to test if telemedicine-based engagement is feasible, safe, and noninferior to the co-located intervention.

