#### 2. Section 1.4: Intervention Arm

**Change:** For participants entering in Part B, the co-located rapid start intervention will be converted to telemedicine rapid-start intervention. Consented participants will have same-day or next-day telemedicine visits with a hepatitis C provider and baseline blood testing will be arranged on a personalized basis utilizing convenient community-based laboratory facilities (including current co-located SSP and commercial laboratories). For participants found to be HCV PCR positive, personal delivery or pick-up of a 28-day supply of sofosbuvir/velpatasvir (Epclusa®) will be

arranged. Telemedicine visits will be arranged two weeks after treatment delivery. For participants who confirm treatment initiation, side effects will be assessed, delivery/pick-up of the final 56-day of medication will be arranged, and week 4 monitoring labs will be offered (no longer required) and arranged.

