### 6. **Section 5.1 :** Schedule of Study Events

**Change:** Week 4 and Week 8 laboratory draws are now changed to optional, to minimize travel and physical contact. Monitoring labs for re-infection have been eliminated, and re-infection will not be analyzed for the telemedicine cohort. Instead, individuals will reach the study endpoint at either SVR 12 or at week 48, whichever comes first. The frequency of medical visits will be unchanged but physical exams will no longer be performed except as possible through telemedicine. Weekly telephone or video check-ins will also continue.

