#### 1.4.2 Intervention Arm

In Part A: Participants randomized to the intervention arm will have a same-day visit with a study physician. Those who are interested in being treated for their HCV, and have no contraindication, will (a) have standard of care baseline laboratory testing drawn and be given a one-week ‘Starter-Pack’ (7 day supply) of sofosbuvir 400mg/velpatasvir 100mg. Subsequent supplies of DAA therapy will be distributed to HCV RNA test positive participants as one 21-day and one 56 day supply to complete a 12-week treatment course. Those participants with negative confirmatory HCV RNA testing will be contacted via telephone and instructed not to begin the medication, and will not be given additional medication supplies.

Participants will be contacted weekly while receiving sofosbuvir/velpatasvir by text message to assess adherence, potential adverse effects, and offered other tele-support as needed. Scheduled study visits will occur at 4 weeks, upon treatment completion or discontinuation (study week 12), study week 16 (corresponding to SVR4), study week 24 (corresponding to SVR12), study week 36, and study week 48. Each study visit will consist of laboratory testing, semi-structured interview, and physician visit. Additional medical visits may be scheduled at the participants’ request. Additionally, each participant will be scheduled for a one-time counseling session for prevention of reinfection during their course of treatment. Referral to harm reduction and/or opioid substitution treatment programs will be provided for interested participants, but utilization of these services is not a condition of enrollment in the study or of HCV treatment provision.

In Part B: Participants will be enrolled in the telemedicine arm, and will have a same-day or next-day telemedicine visit with the hepatitis C provider. Initial evaluation will be either via telephone, video, or in-person at the syringe service program depending on patient preference. Blood testing will be arranged at local community laboratory facilities. Participants with positive HCV RNA will have delivery of a 28 day supply of sofosbuvir/velpatasvir, and a 56 day supply after completion. Weekly check-ins will occur by phone, and participants will have clinical laboratory monitoring at week 4 (optional), week 12, every 12 weeks thereafter until completion of follow up. Participants will complete a short structured survey at weeks 0, 12, 24, 36, and 48, also over video or telephone.

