#### 1.7 Secondary Outcomes

[figure not shown]
1. The proportion of participants who initiate treatment for HCV in the intervention arm compared to the usual care arm by study week 48.
2. The proportion of participants who complete the prescribed course of treatment for HCV in the intervention arm compared to the usual care arm by study week 48.3. The proportion of participants after initiating HCV treatment did not complete it compared to the usual care arm by study week 48.
4. The proportion of participants in both arms who achieve SVR 12, or are RNA negative at baseline, that have HCV reinfection (defined in section 5.5) by study week 48.
5. To characterize the HCV genotype and presence of resistance associated substitutions (RAS) in those treated patients with HCV reinfection or relapse.
6. To examine impact of engagement in HCV treatment on substance use behaviors and injection risk.
7. Qualitative assessment using semi-structured interviews to evaluate the acceptability of the intervention versus usual care, the barriers to initiate and complete treatment, and factors influencing successful treatment outcomes
8. To assess the feasibility, safety, and effectiveness of a tele-medicine based rapid start intervention for hepatitis C treatment in young people who inject drugs.

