## 8.3 Data Analysis

### 8.3.1 Analysis of clinical outcomes data

For the primary analysis, after the completion of part A, we will compare the proportion of patients who achieve SVR12 in each arm using Chi-square or Fishers’ exact testing, using an intention-to-treat approach in which participants are analyzed in the group to which they are randomized. Participants with negative confirmatory HCV RNA PCR tests on study entry will not be included in the analysis.

For secondary analyses, we will:

- Compare the proportion of patients who achieve end-of-treatment response using Chi-square or Fishers’ exact testing
- Compare the proportion of patients who complete treatment, using Chi-square or Fishers’ exact testing
- Compare the proportion of patients who have HCV reinfection, using Chi-square or Fishers’ exact testing
- Describe adherence for participants in the Intervention arm only
- Describe demographic, clinical and behavioral factors for participants who have HCV reinfection or incident HCV infection

We will also perform the same analyses using an “as-treated” approach, in which participants in the intervention arm will not be included if they failed to initiate HCV treatment, or discontinued treatment for reasons clearly unrelated to the treatment intervention (e.g. relocation, incarceration).

After the completion of part B, we will compare the proportion of patients who achieve SVR12 in each Part B telemedicine to (1)Part A intervention (2) Part A control, using Chi-square or Fishers’ exact testing, using an intention-to-treat approach in which participants are analyzed in the group to which they are randomized. Participants with negative confirmatory HCV RNA PCR tests on study entry will not be included in the analysis.

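### Safety of telemedicine delivery is a stated Part B aim, but no adverse-event analysis is planned and side-effect enquiry is partial and inconsistently described

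*Combined protocol and SAP*

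**What the plan says.** **The aim.** Section 0.1 states that Part B outcomes will be used "to test if telemedicine-based engagement is feasible, safe, and noninferior to the co-located intervention". Section 1.7, item 8, makes it a secondary outcome: "To assess the feasibility, safety, and effectiveness of a tele-medicine based rapid start intervention". Neither place names a safety measure, a time point or a threshold.

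**The analysis.** Section 8.3.1 lists, as secondary analyses, end-of-treatment response, completion, reinfection, adherence ("Describe adherence for participants in the Intervention arm only") and a description of participants with reinfection or incident infection. For Part B it plans only the SVR12 comparisons with the two Part A arms.

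**The collection.**
- Section 1.4.2, Part A: participants on drug are contacted weekly "by text message to assess adherence, potential adverse effects, and offered other tele-support as needed".
- Section 5.3, for intervention participants on treatment: "This will be accomplished by weekly secure text messaging consisting of a single item question".
- Section 1.4.2, Part B: "Weekly check-ins will occur by phone". The amendment section (0.2, item 6) says "Weekly telephone or video check-ins will also continue". Neither says what is asked.
- Amendment section (0.2, item 2), at a telemedicine visit two weeks after delivery of drug: "For participants who confirm treatment initiation, side effects will be assessed".
- The Part B schedule of events has a weekly adherence row and no adverse-event row. The week 4 laboratory draw is optional.

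**The concern.** A trial that says it will test whether a mode of delivery is safe needs three things: a defined event, a uniform way of asking about it, and a planned summary. Here the summary is absent, no event is defined, and the asking is described differently in different places.

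Two consequences follow. First, no safety result comes out of the plan as written. Second, if investigators later count whatever was noted, a low count could mean few events or few enquiries, and the records would not distinguish the two. A table can be added after the fact. A question that was never asked cannot.

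The point weighs more in Part B than in Part A, because remote delivery and the optional week 4 draw leave more of the on-treatment safety information to what participants are asked.

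**Working it through.** **1. Is there a safety figure to reproduce?** No. The sample-size section (8.1) concerns SVR12 only. Its 80% power for 11/27 against 78% with 27 per arm reproduces at 80.9% (two-sided 0.05, normal approximation without continuity correction), but it has no bearing on safety.

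**2. Is a safety analysis planned anywhere?** Section 8.3.1 has no entry for adverse events, serious adverse events, laboratory safety or stopping drug because of an event. The contents list goes from 8.3.2 (qualitative data) straight to the references. The text supplied contains no adverse-event definition, grading, collection window or safety population.

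**3. What does the weekly contact ask?**
- *Part A.* Section 1.4.2 gives adherence plus possible adverse effects. Section 5.3 gives one item, under an adherence heading. The two can be squared only if the adverse-effect enquiry is a separate message or question, which neither section says.
- *Part B.* Contact is by telephone or video, so section 5.3's text message does not describe it. Its content is unstated, and the schedule shows it only as adherence.

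**4. What safety information will Part B collect?**
- A side-effect enquiry two weeks after delivery of drug. This is in the amendment section but not in section 1.4.2 or the Part B schedule. A difference between an amendment summary and the body is not in itself an error, but staff working from the body would not find this enquiry.
- A hepatic panel in RNA-positive participants: optional at week 4, not marked optional at weeks 12, 24 and 48.
- Monitoring for hepatitis B reactivation in surface-antigen-positive participants (section 6.5), with no analysis attached.

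So the explicit side-effect enquiry in Part B is one stated occasion in a 12-week course.

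**5. What could a complete record support?** Section 3.0 gives 72 antibody-positive participants over both parts and no Part B number. I assume 10 to 36 treated in Part B. With zero events in n participants:
- exact two-sided 95% upper limit = 1 − 0.025^(1/n)
- chance of seeing at least one event when the true rate is 5% = 1 − 0.95^n

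| n treated (assumed) | Upper limit, 0 events | Chance of ≥1 event at a true 5% rate |
|---|---|---|
| 10 | 30.8% | 40% |
| 20 | 16.8% | 64% |
| 27 | 12.8% | 75% |
| 36 | 9.7% | 84% |

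For n = 27: 1 − 0.025^(1/27) = 0.128. These limits assume that every participant was asked in the same way. Where events go unrecorded, they bound the recorded rate and not the true one.

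**The case against.** The strongest reply is that safety data are being collected. A reader might infer from section 5.3 that Part B events come to light only when a participant volunteers them. The documents do not support that. Section 5.3 describes how adherence is measured by text, and Part B contact is by telephone or video. The amendment section has side effects actively assessed at two weeks, the week 12 hepatic panel is not optional, and hepatitis B reactivation is monitored. In Part A, section 1.4.2 has the weekly text cover adverse effects, and study visits include a physician. This stands: collection is partial and under-specified, not passive.

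Nor should much be made of physical examinations. In the Part A schedule those at weeks 4 and 12 were already only if medically indicated, so between the two schedules only the week 0 examination changes.

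It is also fair to say that section 8.3.1 omits other secondary outcomes (treatment initiation, resistance substitutions, substance use), so the gap is not peculiar to safety. The study calls itself a pilot and uses an FDA-approved regimen. That argues for a modest safety analysis, not for none, since section 0.1 and item 8 commit the trial to a statement about the safety of this delivery model.

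Finally, the limits in the table reflect small numbers and would apply under perfect collection. That is correct. They show how far a safety statement could go, not the damage done by the omission.

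**Conclusion.** The point holds in this form: safety of telemedicine delivery is a named aim, no adverse-event analysis is planned, and side-effect enquiry in Part B is neither uniform nor fully specified. Some safety information will be gathered, but not systematically enough to support a conclusion that the model is safe.

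The primary SVR12 analysis is untouched. What cannot be answered as written is the safety part of item 8.

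On size, no events at all would leave an upper limit between 30.8% (n = 10) and 9.7% (n = 36). This rests on an assumed Part B size and on complete, uniform enquiry. A descriptive rate is the most that item 8 can claim.

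**What to change.** 1. **Reconcile the descriptions.** Make sections 1.4.2, 5.3, the Part B schedule and the two-week enquiry in the amendment section agree on what is asked, when, and by which mode.
2. **Fix the question.** Add one adverse-effect question with set wording to every Part B weekly check-in on treatment. Weekly contact is scheduled only on treatment, so put the same question in the existing week 12 and week 24 contacts, which already carry a questionnaire. Add a matching row to the Part B schedule.
3. **Plan the summary.** In section 8.3.1, report for Part B the proportions with any adverse event, any serious adverse event (by a stated standard definition) and any stop of drug for an adverse event. Give exact 95% intervals and label the table descriptive. State the denominator, for example participants who took at least one dose.
4. **Limit the Part A display.** Part A is analysed on enrolment through March 1, 2020, so a new question cannot repair its records. Show Part A intervention data only where they were recorded, without a formal comparison.
5. **Reword item 8 and section 0.1** to claim a descriptive safety rate.

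The cost is one extra question in contacts that already take place, one table, and a more modest safety claim. The change concerns data collection and reporting only and sets no clinical rule.

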## 5.4 Qualitative and Questionnaire Evaluation

In-person interviews will be conducted for a sample of participants at the end of therapy (week 12), and at week 24, and 48. Participants will be asked to identify factors that promote or hinder engagement in HCV treatment, harm reduction services or substance use treatment. We will also inquire about participants substance use, sexual, and injection risk behaviors pre-, during and post- treatment. Participants who refuse interview will still be offered the HCV treatment. At the end of therapy, participants will be asked about changes in these factors, about uptake of safer injecting practices, engagement in harm reduction or substance use treatment, and the acceptability of the Seek, Test, and Rapid Treatment intervention.

## 5.5 Monitoring for reinfection

Participants in the intervention arm who receive treatment will have two post-treatment HCV RNA PCR tests, at 24 and 48 weeks, to monitor for re-infection after treatment completion. Participants who did

not receive treatment, either because of HCV-negative status or because of other reasons, will have HCV RNA PCR testing at 24 and 48 weeks. All participants in the control arm, regardless of HCV RNA status, will have HCV RNA PCR testing at 24 and 48 weeks, but it is expected that these may not be “post-treatment,” as we expect treatment initiation to be delayed for the control participants.

True reinfection will be defined as a positive HCV RNA PCR with a different HCV genotype, occurring anytime after a documented SVR 12 (negative HCV RNA PCR 12 weeks or more after treatment completion).

Participants who (1) did not have a documented SVR 12 but did have a documented end-of-treatment response or SVR 4, and subsequently have a positive HCV RNA PCR OR (2) have a positive HCV RNA PCR after documented SVR12 with the same genotype as the initial infection, will be classified as possible reinfections. These participants will then be reclassified as either true reinfections or relapses based on viral sequencing of their baseline HCV infection compared to subsequent positive HCV RNA PCRs.

